8.2. Protocol Deviations

Protocol deviations will be categorized as Major and Minor.

Major deviations include those that involve the informed consent process, and the inclusion/exclusion criteria of the study.

Minor deviations include all other noted deviations, i.e. Missed Assessment, Assessment not done in the required timeframe, and other.

9. STATISTICAL METHODS

9.1. Determination of Sample Size

The study sample size of 200 patients is based on treatment of a reasonable number of subjects with the study device to provide a reliable and meaningful assessment of device performance, rather than based upon any statistical hypothesis of an endpoint.

9.2. General Considerations

9.2.1. General Methods

All descriptive statistical analyses will be performed using SAS (Version 9.4 or higher), unless otherwise noted. Derived variables will be programmed by the study programmer/statistician, and then verified by an independent programmer/statistician (e.g., age or height conversions). The program review also will include a check whether analyses conform to specifications of the SAP. All output will be incorporated into Microsoft Word files and formatted as to the appropriate page size(s).

All primary and secondary endpoints will be evaluated using descriptive statistics only. No hypothesis tests will be performed.

Statistics for continuous outcomes will include N, mean, median, standard deviation, minimum, and maximum. Binary outcomes will be summarized using frequencies, percentages and two-sided exact 95% confidence intervals for the primary and secondary endpoints. For categorical variables, the number and percentage within each category of the parameter will be calculated.

The baseline demographic and clinical characteristics, lesion characteristics, procedure information will be summarized by descriptive statistics for the ITT population.

9.2.2. Adjustments for Covariates

No adjustment for covariates will be made.

9.2.3. Handling of Dropouts or Missing Data

Only enrolled subject data which are collected will be included in the analysis. All efforts will be made to reduce missing data. In general, missing data will not be imputed in this study unless partial dates for special variables as described in Section 9.2.3.1. Details of imputing partial dates are described next.

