### **5.3.4 Index Procedure**

The start of the index procedure is defined as the time of sheath insertion. If a previously placed sheath is used (i.e., from an earlier diagnostic procedure), index procedure start time is defined as the time of guide catheter insertion into sheath for wiring the target lesion. During cardiac catheterization, the following procedures and assessments must be completed.

- Perform angiography according to the Angiographic Core Laboratory procedure guidelines.
- Confirm angiographic eligibility criteria.
- Treat the non-target lesion, if any, prior to treatment of the target lesion as described in Section 6.1.
- If treatment of non-target lesion was successful, continue with enrolling the subject in the study.
- If the subject is enrolled, treat subject accordingly with the Scoreflex NC catheter and perform angiography according to the Angiographic Core Laboratory procedure guidelines and collect study related data.
- If more than one lesion is treated with the Scoreflex NC catheter, similarly perform angiography according to the Angiographic Core Laboratory procedure guidelines and collect study related data.

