6.2.2. Secondary Endpoints

The secondary endpoints consist of angiographic procedural efficacy, clinical, and peri-procedural endpoints.

The secondary angiographic procedural efficacy endpoint is measured and defined as follow:

- Final diameter stenosis $\leq 50\%$ in at least one of the Scoreflex NC attempted lesions following completion of the interventional procedure, including adjunctive stenting

The secondary clinical endpoints which are measured through hospital discharge are as follows:

- In-hospital Major Adverse Cardiac Events (MACE), a composite of the following:
 - All death (cardiac and non-cardiac)
 - Myocardial infarction (MI)
 - Clinically indicated Target Lesion Revascularization (TLR)
- In-hospital stent thrombosis (ST) within the target vessel
- Clinically significant arrhythmias (requiring intervention)

The secondary peri-procedural endpoints are measured through hospital discharge and defined as follows:

- Occurrence of Scoreflex NC study balloon rupture
- Improvement in Minimum Lumen Diameter (MLD) following use of Scoreflex NC coronary dilatation catheters (measured by QCA)

Both MI and ST are to be determined by the Academic Research Consortium (ARC) classification criteria. MI will be classified into various types including the 99th percentile upper reference limit (URL) decision limits for biomarkers employed.

Myocardial Infarction will be defined as:

- Q-Wave MI: Development of new (i.e., not present on the subject's ECG before allocation) pathological Q-waves in 2 or more leads lasting 0.04 seconds with post-procedure CK-MB levels elevated above normal.
- Non-Q-Wave MI: Elevation of post-procedure CK-MB levels to >3.0 times ULN without new Q-waves.

For subjects undergoing bypass surgery, a peri-operative MI will be defined as follows:

a) Total CK-MB $>5\times$ ULN.

or

b) Presence of new pathologic Q-waves as defined above.

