9.4. Primary Endpoint Analysis

The primary endpoint is a device procedural success endpoint based on a composite of the following components:

- Successful delivery, inflation, deflation, and withdrawal of the study balloon
- No evidence of vessel perforation, flow limiting dissection (grade C or higher) or reduction in TIMI flow from baseline as related to the Scoreflex NC study balloon
- Final TIMI flow grade of 3 at the conclusion of the PCI Procedure

A patient's procedure is considered a success if all of three components are successful.

Number and percentages of each component above and the overall composite primary endpoint will be calculated and presented, by both patient level and lesion level, with two-sided 95% confidence intervals at index procedure, based on the Intent-to-Treat (ITT) and Per-Protocol (PP) population, respectively.

Because this study is a prospective, open label, multi-center, single arm, observation study, no formal hypothesis testing will be performed.

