13. STATISTICAL TABLES TO BE GENERATED

- Table 1. Patient Disposition -ITT Population
- Table 2. Demographics and Clinical Characteristics -ITT Population
- Table 3. Baseline Patient Medical History - ITT Population
- Table 4. Baseline Patient Laboratory Value -ITT Population
- Table 5. Baseline Patient Medications -ITT Population
- Table 6. Procedure -Per Patient -ITT Population
- Table 7. Lesion Characteristics (Lesion based) -ITT Population
- Table 8. Scoreflex NC Device Usage (Lesion based) -ITT Population
- Table 9. Protocol Deviations -ITT Population
- Table 10.1.1. Summary of Primary Endpoint Analysis by Subcomponents at Patient Level -ITT Population
- Table 10.1.2. Summary of Primary Endpoint Analysis by Subcomponents at Lesion Level -ITT Population
- Table 10.2.1. Summary of Primary Endpoint Analysis by Subcomponents at Patient Level -PP Population
- Table 10.2.2. Summary of Primary Endpoint Analysis by Subcomponents at Lesion Level -PP Population
- Table 11.1. Summary of Secondary Endpoint Analysis at Patient Level -ITT Population
- Table 11.2. Summary of Secondary Endpoint Analysis at Patient Level -PP Population
- Table 12. Summary of Primary Endpoint Analysis by Reason for use of Scoreflex NC at Patient Level -ITT Population
- Table 13.1 Summary of Adverse Events -ITT Population
- Table 13.2 Summary of Relatedness of MACE to the Procedure and the Device -ITT Population
- Table 14.1 Baseline Angiographic Findings -ITT Population
- Table 14.2 Quantitative Angiographic Findings -ITT Population
- Table 14.3 Post Coronary Dilatation Catheter Morphology -ITT Population
- Table 14.4 Final Post-Procedure Morphology -ITT Population

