14. DATA LISTINGS TO BE GENERATED

Listing 1. Demographics -ITT Population

Listing 2. Primary Safety and Efficacy Endpoint at Index Procedure -ITT Population

Listing 3. Secondary Endpoint -ITT Population

Listing 4.1 Angiographic Core Lab at Pre-Procedure -ITT Population

Listing 4.2 Angiographic Core Lab at Post-Scoreflex NC Coronary Dilation Catheter
-ITT Population

Listing 4.3 Angiographic Core Lab at Post Procedure -ITT Population

Listing 5. Medical History -ITT Population

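### Could a missing post-balloon reading pass as a success in the primary composite?

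*SAP*

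**What the plan says.** SAP 9.4 builds the primary endpoint from three components. The second reads "No evidence of vessel perforation, flow limiting dissection (grade C or higher) or reduction in TIMI flow from baseline", as related to the study balloon. The third requires a documented final TIMI grade of 3. A patient's "procedure is considered a success if all of three components are successful".

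The primary analysis set is ITT, defined in SAP 8.1 as everyone consented and enrolled. Only the per-protocol set requires primary endpoint data to be available. On missing data, SAP 9.2.3 states: "Only enrolled subject data which are collected will be included in the analysis". It allows imputation for partial dates only. Protocol section 9 (Primary end-point) likewise pairs ITT with no imputation. SAP 9.3 has the disposition table count the subjects with available primary endpoint data.

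Stents may follow the balloon: the secondary angiographic endpoint in SAP 6.2.2 is read "following completion of the interventional procedure, including adjunctive stenting". The SAP keeps the post-balloon and final time points apart. Table 14.3 is "Post Coronary Dilatation Catheter Morphology -ITT Population" and Listing 4.2 is "Angiographic Core Lab at Post-Scoreflex NC Coronary Dilation Catheter", while Table 14.4 and Listing 4.3 cover the end of the procedure.

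**The concern.** Take a subject whose balloon was delivered and withdrawn successfully and whose final TIMI flow is 3, but for whom nobody has a reading between balloon and stent. Component 2 asks for an absence, and a missing film also shows no evidence of injury. Once a lesion is stented, the final film may no longer show a dissection or flow drop that the balloon caused, so the intermediate reading matters.

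Three scorings then seem open:

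- **Success**, because no evidence was recorded.
- **Left out**, because only collected data are used.
- **Failure**, because all three components must be met and ITT covers everyone enrolled.

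SAP 9.4 does not tie component 2 to the post-balloon time point and does not say whether the investigator or the core laboratory decides it. Availability of the primary endpoint is not defined for such a subject.

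The headline rate and its exact interval would be at stake. Under the first scoring any error favours the device, on the component meant to catch balloon injury. The subject would also count as available in the disposition table and appear as an ordinary success in Listing 2, "Primary Safety and Efficacy Endpoint at Index Procedure -ITT Population".

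**Working it through.** **Plan's own figures.** There is no computed figure to reproduce. SAP 9.1 says that 200 subjects was not derived from a hypothesis, and the documents give neither an expected success rate nor a missing rate. The nearest benchmark is the FX miniRAIL pivotal trial in Protocol Table 2.0: 235/248 = 94.8%, for another device and another endpoint. It suggests about 10 failures in 200 as an illustration.

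**Inputs.** N = 200 (SAP 9.1) and two-sided exact 95% intervals (SAP 9.2.1). Assumed: f documented failures, and m subjects with components 1 and 3 met, no documented failure and no post-balloon reading.

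**Formulas.**

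- Success: (200 − f)/200
- Left out: (200 − m − f)/(200 − m)
- Failure: (200 − m − f)/200

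**Results with f = 10** (Clopper-Pearson intervals):

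| m | Success | Left out | Failure |
|---|---|---|---|
| 0 | 190/200 = 95.0% (91.0–97.6) | same | same |
| 4 | 190/200 = 95.0% (91.0–97.6) | 186/196 = 94.9% (90.8–97.5) | 186/200 = 93.0% (88.5–96.1) |
| 10 | 190/200 = 95.0% (91.0–97.6) | 180/190 = 94.7% (90.5–97.4) | 180/200 = 90.0% (85.0–93.8) |
| 20 | 190/200 = 95.0% (91.0–97.6) | 170/180 = 94.4% (90.0–97.3) | 170/200 = 85.0% (79.3–89.6) |

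**Success against left out.** The gap is f·m / [200·(200 − m)].

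- f = 10, m = 4: 40/39,200 = 0.1 points
- f = 10, m = 20: 200/36,000 = 0.6 points
- f = 5, m = 20: 100/36,000 = 0.3 points
- f = 20, m = 20: 400/36,000 = 1.1 points (90.0% against 88.9%)

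**Success against failure.** The gap is m/200, or 0.5 points per unread subject. All the large differences come from this comparison.

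**Which scoring the text supports.** Scoring an unread component as failed gives a value to something not observed. Scoring it as passed does the same, unless a missing reading is treated as a collected finding of no injury. Protocol section 9 and SAP 9.2.3 both decline to fill in missing values, so leaving the subject out is the reading that respects both.

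**Hidden failures.** If k of the m = 20 unread subjects really had a component 2 failure, the true rate is (190 − k)/200. Read subjects fail at 10/180 = 5.6%, which applied to 20 gives about 1 failure.

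- k = 1: 189/200 = 94.5%, close to both reported rates.
- k = 5 (25% of the unread): 185/200 = 92.5%, inside both reported intervals (91.0–97.6 and 90.0–97.3).
- k = 10 (50% of the unread): 180/200 = 90.0%, below the lower limit of 91.0 under success and level, to one decimal, with the lower limit of 90.0 under left out.

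Leaving the subjects out does not cure this either: at k = 5 it reports 94.4% where the truth is 92.5%. A rule written into the SAP would change the reported rate by 0.6 points and would not recover what was never read.

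**The case for a change.** The strongest case for a change is that a ban on imputation does not settle the matter. A programmer who derives component 2 as the absence of an event flag would say that nothing was imputed, yet a missing reading has become a success. With no test, the rate and its interval are the study's main result. The SAP gives detailed rules for partial medication and adverse event dates but none for a composite that cannot be determined. Denominators do move: in the FX miniRAIL trial 263 were enrolled and 248 analysed, and 235/263 would be 89.4% rather than 94.8%. The documents do not say why 15 are absent.

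Part of this stands. Neither document names the deciding reader or the time point for component 2, and the ITT definition is not reconciled with the collected-data rule for this subject.

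The consequences are weaker than they look:

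- **Few readings should be missing.** Protocol 5.3.4 tells sites to "treat subject accordingly with the Scoreflex NC catheter and perform angiography according to the Angiographic Core Laboratory procedure guidelines". The endpoint is acute and observed in the procedure room.
- **Injury has other routes into the data.** Protocol 5.3.5 requires procedural information, stent use and adverse events on the CRF. Section 7 requires every adverse event up to discharge to be recorded, and section 11.6 has monitors review the efficacy endpoints. An injury the operator sees does not depend on a core laboratory film.
- **A shortfall can be seen.** Table 14.3 and Listing 4.2 report the post-balloon time point, and Tables 10.1.1 and 10.2.1 report each component separately.
- **Some detail may lie elsewhere.** The core laboratory guidelines and the table shells, which SAP section 12 says were updated for version 2.0, are not among the documents.

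The FX miniRAIL comparison shows what scoring absent subjects as failures can do. It does not show that this plan scores them so, or that the absences there concerned angiographic readings.

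**Conclusion.** The gap is real but narrow, and no change to the plan follows. It concerns only a subject with no documented failure, a documented final TIMI 3 and no post-balloon reading. If the final film is missing too, component 3 has no reading either, and scoring the subject as a success is no longer open. The plan's rules on collected data and imputation lead an analyst to leave such a subject out.

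With 10 assumed failures in 200, that choice differs from scoring as success by 0.1 points at 4 unread and 0.6 points at 20 unread. With 20 assumed failures and 20 unread it differs by 1.1 points. Larger effects need either the failure scoring, which the no-imputation text disfavours, or a hidden failure rate of 25% to 50% among the unread, which no document supports and which leaving subjects out would not correct. SAP 6.2 and 9.2.1 set no hypothesis or test, so no decision turns on the difference.

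This rests on the assumption that unread films are few. The documents give no missing rate; the range examined is 0 to 20 of 200.

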FX miniRAIL RX PTCA	
Procedural Success: (in-hospital) 94.8% (235/248)
 
< 50% final diameter stenosis in at least one of the attempted lesions with death, Q-wave or non-Q-wave MI, or emergency CABG during the hospital stay
 
Clinical Success: 97.1% (231/238)
 
Freedom from MACE – death, Q wave or non-Q wave MI, or TLR at the 14-day follow-up.
 
 
• Seven (7) subjects with at least one MACE event.               
 
• Six (6) of the patients experienced MACE event(s) while in-hospital,
 
• One (1) experienced a MACE event, a non-Q wave MI related to a subsequent non-target lesion revascularization, not due to the FX miniRAIL procedure
 
 
 
	263 enrolled	P020037 

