#### **4.1 Selection and Withdrawal of Subjects**

Once the subjects have signed the Institutional Review Board (IRB) approved study informed consent form (ICF) and research authorization forms (RA/HIPAA) and have met all general inclusion and exclusion criteria, the subjects will be considered eligible to be enrolled in the study to receive treatment with the Scoreflex NC dilatation catheter. A subject is considered enrolled in the study upon insertion of the investigational device into a guide catheter. Upon enrollment, a subject identification number will be assigned to each subject in a consecutive manner within each clinical site.

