### Primary end-point

The primary endpoint will be assessed in the intent-to-treat (ITT) patient population. Every effort will be made to reduce bias by obtaining as much follow-up as possible. No imputation of missing data is done for the primary analysis.

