8.1. Analysis Populations

The primary analysis set is the ITT population. The ITT population includes all consented and enrolled subjects.

The PP population is defined as all enrolled subjects who received a Scoreflex NC device with availability of data of the primary endpoint and without any major protocol violations including the violation of inclusion or exclusion criteria as shown below. The PP population will be used for confirmatory analysis of efficacy endpoints. Categories of Major protocol deviations are defined in Section 8.2.

The following are inclusion and exclusion criteria.

Inclusion Criteria

1. Subject is ≥ 18 years of age
2. Subject or a legally authorized representative must provide written informed consent prior to any study related procedures.
3. Subject must agree not to participate in any other clinical study during hospitalization for the index procedure that would interfere with the endpoints of this study.
4. Subjects must have a single or double vessel coronary artery disease and clinical evidence of ischemic heart disease, such as CAD, stable / unstable angina or silent ischemia

Angiographic Inclusion Criteria

5. Subject must have de novo or restenotic lesion(s) in native coronary arteries, including in-stent restenosis suitable for percutaneous coronary intervention.
6. A maximum of two lesions, including at least one target lesion, in up to two coronary arteries.
7. Target lesion must have a reference vessel diameter (RVD) between 1.75 and 4.0 mm by visual estimation.
8. Target lesion(s) must have a diameter stenosis of $\geq 70\%$ by visual estimation and may include chronic total occlusions (CTO).

Exclusion Criteria

General Exclusion Criteria

1. Subject with a known hypersensitivity or contraindication to aspirin, heparin, bivalirudin, anti-platelet medications, or sensitivity to contrast media which cannot be adequately premedicated

2. Subject with known diagnosis of STEMI or NSTEMI at index presentation or within 7 days of study screening
3. Subject with known pregnancy or is nursing. Women of child-bearing potential should have a documented negative pregnancy test within 7 days before index procedure
4. Planned or actual target lesion treatment with an unapproved device, atherectomy, laser, cutting balloon or thrombectomy during the index procedure
5. A serum creatinine level > 2.0 mg/dl within 7 days prior to index procedure
6. Cerebrovascular accident (CVA) within the past 6 months

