9.5. Secondary Endpoint Analyses

The secondary endpoints consist of angiographic procedural efficacy, clinical, and peri-procedural endpoints.

Binary secondary endpoint will be summarized using frequency, percentage, and two sided exact 95% confidence interval through hospital discharge based on the Intent-to-Treat (ITT) and Per-Protocol (PP) population, respectively.

For the continuous binary endpoint, i.e. Improvement in Minimum Lumen Diameter, the simple statistic description such as mean, median, and standard deviation will be presented.

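### The ITT rate for final diameter stenosis ≤50% has no rule for subjects without a final reading; read literally, SAP 9.2.3 drops them, which may favour the device if readings are missing because procedures failed

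*SAP*

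**What the plan says.** The endpoint (SAP 6.2.2; Protocol 6.2) is met when the final diameter stenosis is 50% or less "in at least one of the Scoreflex NC attempted lesions following completion of the interventional procedure, including adjunctive stenting". It is therefore scored per subject, on attempted lesions, after all treatment.

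**Population.** SAP 8.1: "The ITT population includes all consented and enrolled subjects". Protocol 4.1: "A subject is considered enrolled in the study upon insertion of the investigational device into a guide catheter". A subject whose procedure is abandoned after that moment is still ITT. Protocol section 9 places all secondary endpoints in ITT. (The protocol synopsis uses a different, undefined term for that population; I follow section 9 and the SAP.)

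**Analysis.** SAP 9.5: "Binary secondary endpoint will be summarized using frequency, percentage" and an exact two-sided 95% interval, in ITT and in PP. Table 11.1 is the ITT display.

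**Missing data.** SAP 9.2.3: "Only enrolled subject data which are collected will be included in the analysis", followed by "In general, missing data will not be imputed in this study unless partial dates for special variables as described in Section 9.2.3.1". The protocol's own sentence is narrower: "No imputation of missing data is done for the primary analysis". It says nothing on secondary endpoints.

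**Not stated anywhere:** the denominator of this rate, how an attempted lesion without a final reading is scored, or a sensitivity analysis for such subjects.

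**The concern.** ITT as defined keeps every enrolled subject. The missing-data rule keeps only those with a value. For this endpoint the two can give different denominators, and the title of Table 11.1 would not tell a reader which was used.

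A final reading can be absent for two quite different reasons. The film may exist but be unreadable, which need say nothing about the result. Or the procedure may have been cut short by a complication, emergency surgery or death before the last angiogram. A subject of the second kind had a lesion attempted and was never shown to reach ≤50%, yet would count neither for nor against the device. The SAP does not separate the two.

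With no hypothesis and no performance goal, the reported percentage and its interval are the whole result for this endpoint, so the denominator should be settled in advance.

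**Working it through.** **Inputs.** N = 200 (SAP 9.1). The plan gives no expected rate and no expected number of missing readings for this endpoint, so it has no figure of its own to reproduce. The number missing, *m*, and the observed rate, *p*, below are assumptions. Intervals are Clopper-Pearson 95%.

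**Step 1: three rates for one data set.** Let *x* be the subjects shown to meet ≤50%.
- Observed case: x/(200 − m)
- Worst case, missing counted as not meeting ≤50%: x/200
- Best case, missing counted as meeting it: (x + m)/200

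| Assumed missing | Observed case | Worst case | Best case |
|---|---|---|---|
| 4 | 186/196 = 94.9% (90.8 to 97.5) | 186/200 = 93.0% (88.5 to 96.1) | 190/200 = 95.0% (91.0 to 97.6) |
| 11 | 179/189 = 94.7% (90.5 to 97.4) | 179/200 = 89.5% (84.4 to 93.4) | 190/200 = 95.0% (91.0 to 97.6) |

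With 11 missing, the observed-case figure lies 94.7 − 89.5 = 5.2 points above the worst case and 95.0 − 94.7 = 0.3 points below the best case.

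**Step 2: sign of the bias.** Let *q* be the true failure share among the missing. The all-enrolled rate is [(200 − m)p + m(1 − q)]/200, so

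bias = p − all-enrolled rate = (m/200) × [q − (1 − p)].

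Take p = 0.95 and m = 10, so that m/200 = 0.05:

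| q | Bias, percentage points |
|---|---|
| 0 | 0.05 × (0 − 0.05) = −0.25 |
| 0.05 | 0 |
| 0.25 | +1.0 |
| 0.50 | +2.25 |
| 1 | +4.75 |

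The bias is upward only if the missing subjects fail more often than the observed ones. It is zero if they fail equally often. The possible overstatement is much larger than the possible understatement.

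**Step 3: an analogy from the protocol.** Protocol 2.6.1, Table 2.0, gives procedural success in an earlier device's trial as 235/248. Check: 235/248 = 94.8%, as stated (91.2 to 97.2). The same table gives 263 enrolled, so 263 − 248 = 15 subjects (15/263 = 5.7%) are outside the denominator. The all-enrolled rate lies between 235/263 = 89.4% (85.0 to 92.8) and (235 + 15)/263 = 95.1%. The same share of 200 is 0.057 × 200 ≈ 11, which is where the 11 in Step 1 comes from. It is only an analogy. That endpoint also required freedom from death, MI and emergency CABG during the stay, and the documents do not say why the 15 are absent.

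**The case against.** The strongest reply has four parts.

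1. *The reduced denominator is inferred.* SAP 9.2.3 does not spell it out for this endpoint, and SAP 8.1 and 9.5 can be read as keeping all enrolled subjects. The table shells are not in the text available, so the displayed denominator cannot be checked. This stands: the point is what the rule does when read literally, and that no other passage overrides it.

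2. *Few subjects would be affected.* The result is read after adjunctive stenting, so failure of the study balloon alone removes nobody. Protocol 5.3.5 makes a final angiogram part of finishing the procedure. A subject with two target lesions is a success if one is read and qualifies. This also stands, and the documents give no expected frequency.

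3. *Bad outcomes remain visible elsewhere.* Death, MI and clinically indicated TLR count in MACE on ITT. Perforation, flow-limiting dissection and failed delivery defeat the primary composite. Listings 3 and 4.3 would let someone count missing readings by hand. This limits the harm, but it does not correct the rate in Table 11.1 or its interval.

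4. *The SAP does not contradict the protocol.* The protocol is silent on imputation for secondary endpoints, so the SAP may set its own rule. I agree. It follows only that the protocol's sentence on the primary analysis does not settle the question here.

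A reader might go further and infer that the rate *is* biased upward. The documents do not support that: the sign depends on why readings are missing, and purely technical loss gives about zero bias. Nor do they show that a core-laboratory QCA reading is part of the endpoint definition. QCA of percent diameter stenosis appears in the protocol's general statistical text, whereas the endpoint list attaches QCA only to minimum lumen diameter.

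**Conclusion.** The point holds in conditional form. The ITT label and the collected-data-only rule do not fit together for final diameter stenosis ≤50%, and nothing planned shows the effect on the rate. The rate and its exact interval may be too favourable if missing readings follow procedural failure.

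Under the assumption of 11 missing of 200, a reported 94.7% could stand for anything from 89.5% to 95.0% of enrolled subjects. With 4 missing, 94.9% could stand for 93.0% to 95.0%. With no readings missing, there is no effect. The earlier trial's 15 uncounted subjects should not be read as evidence of missing final films.

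This is a cheap improvement and not a threat to the study's main conclusion. The endpoint is secondary and descriptive, and no test, error rate or decision rule depends on it.

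**What to change.** In SAP 9.2.3 and 9.5, state that the ITT denominator for this endpoint is all enrolled subjects. In Table 11.1 show, each with its exact 95% CI:
- the observed-case rate, with its denominator;
- the rate with every missing final reading counted as not meeting ≤50%;
- the best-case bound, with missing readings counted as meeting it.

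Add the number of ITT subjects without a final reading, by reason: procedure stopped, film not evaluable, other.

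The cost is a sentence in the SAP and one or two extra table lines; the rates need no new data. The second figure will be somewhat less favourable, and it is conservative for films lost for technical reasons, which is why the best-case bound and the reasons should stand beside it.
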